14.6 Safety

SS will be used as the safety analysis set. Safety will be analyzed by the analysis groups and Day 1 of each period will be considered as the baseline. Day 1 of Period I will be considered as the baseline for the evaluation of the long-term administration of R788. In addition, the analysis for the Non-dosing period and Period III will be performed only for "14.6.1 Adverse events and adverse drug reactions" and "14.6.2 ITP Bleeding Score", and the analysis for R788 treatment period will be performed only for "14.6.1 Adverse events and adverse drug reactions."

14.6.1 Adverse events and adverse drug reactions

The data on adverse events and adverse drug reactions will be analyzed as follows. Adverse events and adverse drug reactions that occur after the dosing of R788 will be analyzed in the evaluation of the R788 treatment period.

1) Incidence rate of adverse events and adverse drug reactions

The number of events, number of subjects with events, and incidence rate with two-sided 95% exact confidence interval (Clopper-Pearson) will be presented for adverse events and adverse drug reactions. The difference in incidence rate between the groups and its two-sided 95% exact confidence interval will be presented.

2) Incidence of adverse events and adverse drug reactions (major events)

The number of events, number of subjects with events, and incidence rate will be presented for the overall adverse events and adverse drug reactions, events leading to death, serious events excluding death, events leading to discontinuation, events leading to interruption, events leading to dose reduction, and events of special interest.

3) Adverse events and adverse drug reactions

The number of events, number of subjects with events, and incidence rate will be presented for the overall adverse events and adverse drug reactions, primary System organ classes (SOCs) and Preferred terms (PTs). The same analysis will be performed for adverse events and adverse drug reactions of special interest.

4) Severity of adverse events and adverse drug reactions

The number of events by severity will be presented for the overall adverse events and adverse drug reactions, primary SOCs and PTs. The same analysis will be performed for adverse events and adverse drug reactions of special interest.

14.6.2 ITP Bleeding Score

1) Summary statistics will be presented for the mean and total scores of the anatomical sites (9 sites except Skin [Hx] and Oral [Hx]) and distribution of the maximum score will be presented.

14.6.3 ECOG performance status

1) The frequency distribution of scores will be presented.

14.6.4 Vital signs

- 1) For vital signs (systolic blood pressure, diastolic blood pressure, pulse rate, and body temperature), the summary statistics of measured values and changes from the baseline will be presented. Scatter plot of measured values before and after administration will be presented.
- 2) The maximum systolic blood pressure after the dosing of the study treatment in each period will be categorized into < 140 mmHg, \geq 140 mmHg to < 160 mmHg, \geq 160 mmHg to < 180 mmHg, and \geq 180 mmHg and frequency distribution will be shown.
- 3) The maximum diastolic blood pressure after the dosing of the study treatment in each period will be categorized into $< 90 \text{ mmHg}, \ge 90 \text{ mmHg}$ to $< 100 \text{ mmHg}, \ge 100 \text{ mmHg}$ to < 110 mmHg, and $\ge 110 \text{ mmHg}$, and frequency distribution will be shown.
- 4) For systolic and diastolic blood pressure, frequency distribution of the number of times of systolic blood pressure ≥ 140 mmHg or diastolic blood pressure ≥ 90 mmHg after the dosing of the study treatment in each period will be shown. The number of times of systolic blood pressure ≥ 160 mmHg or diastolic blood pressure ≥ 100 mmHg will also be presented in the same manner.

14.6.5 Laboratory and immunoglobulin tests

- 1) Summary statistics will be presented for quantitative values and changes from the baseline. Scatter plot of measured values before and after administration will be presented.
- 2) The number and percentage of subjects will be presented for qualitative parameters.
- 3) Shift tables before and after administration will be presented.
- 4) The maximum ALT or AST value after the start of the study treatment in each period will be categorized into $\leq 3 \times \text{ULN}$, $\geq 3 \times \text{ULN}$ to $\leq 5 \times \text{ULN}$, $\geq 5 \times \text{ULN}$ to $\leq 10 \times \text{ULN}$, and $\geq 10 \times \text{ULN}$, and frequency distribution will be presented.

14.7 Pharmacokinetics

PKS will be used as the pharmacokinetic analysis set.

14.7.1 Plasma drug concentration

1) Summary statistics of the plasma concentrations of R406 (active metabolite) will be presented.

14.8 Timing of Analysis

The statistical analysis will be performed with the data in Period I when the data in Period I are locked. The data until the date of data cutoff will be analyzed after all subjects complete Period II.

15. Agreement on and Amendment to the Protocol

15.1 Agreement on the Protocol

The principal investigator must write his or her name and seal or sign, and date the protocol or an alternative document in order to prove that the principal investigator has agreed to the contents of the protocol and agreed to comply with the protocol.

15.2 Amendment to the Protocol

The sponsor must revise the protocol, where necessary, when the sponsor becomes aware of important information to ensure the quality, efficacy, and safety of the study drug or to conduct the study proper manner. When the protocol is revised and even when the protocol is revised by the order of the head of the study institutions based on the opinion from the IRB, the sponsor must obtain agreement with the principal investigator.

The investigator should not implement any deviation from or change to the protocol without prior documented agreement between the principal investigator and the sponsor, and prior review and documented approval from the IRB of an amendment, except where necessary for medical emergency such as to eliminate an immediate hazard(s) to subjects, or when the change involves only administrative aspects of the study.

15.3 Protocol Deviations

If a deviation from or change to the protocol is implemented to eliminate an immediate hazard(s) to subjects or for other medical emergency prior to obtaining approval, the principal investigator must, as soon as possible, submit the deviation or change with its reason(s) and, if appropriate, the proposed protocol amendment to the sponsor, the head of the study institution, and to the IRB via the head of the study institution for approval. The principal investigator also should obtain approval from the head of the study institution, as well as a documented agreement with the sponsor via the head of the study institution. In addition, the investigator should document all deviations from the protocol.

16. Direct access to Source Documents

16.1 Source Documents

A "source documents" is defined as a document, data, and record to create a document such as a CRF. Specifically, that is a necessary record to allow reconstruction of the course of events and evaluation of the study, including the informed consent form, medical records, test/examination data, and a history of the study drug administration. The study institution should consult with the sponsor to identify source documents.

16.2 Direct Access

The head of the study institution and the principal investigator should accept monitoring and audit by the sponsor, and investigations by the IRB and regulatory authorities of Japan and other countries, and make available for direct access the source documents.

The sponsor should confirm that each subject has consented in written to allow the direct access to his or her source clinical records at the time of such monitoring, audit, or investigations by the IRB and regulatory authorities of Japan and other countries.

16.3 Consistency of a Case Report From with the Source Documents

The sponsor should check the CRF from created by principal investigator against the study-related documents such as source documents and confirm that both are accurate.

The CRF should be consistent with the source documents. If any discrepancy is found, the principal investigator should create a document to explain the reason(s) and submit to the sponsor. The study institution should retain a copy of the document.

17. Quality Control and Assurance for the Study

The sponsor will implement quality control and assurance for the study in accordance with the standard operating procedures. The sponsor's auditor should assess whether or not this study is being conducted in compliance with the GCP, the protocol and the operating procedures independently, separating from the routine monitoring and quality control functions in the study.

18. Ethics

18.1 Compliance with GCP

This study will be conducted in accordance with Article 14 (3) and Article 80 (2) of the Act on Securing Quality, Efficacy and Safety of Products Including Pharmaceuticals and Medical Devices and any other relevant standards for clinical studies of drug, which have been specified by the Minister of Health, Labour and Welfare, "Ministerial Ordinance on Good Clinical Practice for Drugs" that was established as the standards stipulated by the ministerial ordinance, and the protocol consistent with the ethical principles that have their origin in the latest Declaration of Helsinki.

18.2 Subject Confidentiality Considerations

The head of the study institution should take necessary measures to ensure the subject's confidentiality. The confidentiality of records related to subjects (e.g., CRFs) must be protected using subject identification codes, and the subject's right should be fully taken into account. The monitor, the auditor, the IRB, and regulatory authorities must maintain subject information as confidential when they access the source documents.

18.3 Compensation to Subjects

1) In the event of study-related health damages in a subject, the study institution must provide treatment and take any other necessary procedures.

2) Regarding the study-related health damages, if the subject claims compensation or indemnification to the study institution or there is such a possibility, the study institution must immediately notify the sponsor and strive to resolve the problem together.

- 3) The sponsor must compensate the study-related health damages in accordance with the compensation regulations set by the sponsor.
- 4) In the event of study-related health damages for which indemnity liability arises later, the compensation should be made at the liable person's own risk and expense.
- 5) The sponsor must purchase insurance for compensation or indemnification described above.

19. Data Handling and Records Retention

19.1 Case Report from Creation and Submission

In this study, clinical study data including investigations, observations, tests and evaluations will be electronically collected and recorded, creating the subject's CRFs. The investigator should create the CRF for each subject who provided informed consent, and the principal investigator will confirm the all record. Data on platelet count, rescue therapy, compliance with the study drug, vital signs (systolic and diastolic blood pressure), diarrhea and neutrophil count should be recorded in the CRFs generally within 3 days (excluding Saturday, Sunday, and holidays) after the data become available. For subjects who do not enter the Period I, demographics (excluding those related to the inclusion/exclusion criteria), tests/examinations and evaluations performed during the screening period, adverse events, and study discontinuation will be collected and recorded. For the creation method of CRF, the separate documented procedure is to be followed.

19.2 External Data

If the results measured at external laboratories are obtained as electronic data, the data should be obtained directly from external laboratories. For the method and timing of the data creation, the written procedure established at the external laboratory should to be followed.

19.3 Records Retention

19.3.1 Study institution

The head of the study institution must retain all documents and records associated with this study until the sponsor notifies the study institution that such documents and records are no longer needed. The head of the study institution or the records retention manager must take measures to avoid any loss or destroying these records during retention and to provide them upon request.

The principal investigator must retain all documents associated with the conduct of the study in accordance with the instructions from the head of the study institution.

19.3.2 Institutional Review Board

The founder of the IRB must retain all documents and records associated with this study until the sponsor notifies the founder that such documents and records are no longer needed. These

Protocol No.: R788-1301

Version: 1.0

records should be readily available to be provided upon request from the regulatory authorities.

Appendix 2 Immune Thrombocytopenic Purpura Bleeding Scale

	Bleeding score					
Site	0	1	2			
Skin (Physical Examination	None	1–5 bruises and/or	> 5 bruises with size			
[PE])		scattered petechiae	> 2 cm and/or diffuse			
			petechiae			
Oral (PE)	None	1 blood blister or	Multiple blood blisters			
		> 5 petechiae or gum	and/or gum bleeding			
		bleeding that clears				
		easily with rinsing				
Skin (Hx)	None	1–5 bruises and/or	> 5 bruises with size			
		scattered petechiae	> 2 cm and/or diffuse			
			petechiae			
Oral (Hx)	None	1 blood blister or	Multiple blood blisters			
		> 5 petechiae and/or	and/or gum bleeding			
		gum bleeding < 5 min	> 5 min			
Epistasis None		Blood when blowing nose and/or epistaxis	Bleeding > 5 min (per			
			episode)			
G 1 (GD)		< 5 min (per episode)	G 11 1			
Gastrointestinal (GI)	None	Occult blood	Gross blood			
Urinary (U)	None	Microscopic	Macroscopic			
G 1 1 (GVD)	NT (1 ' 1)	(+ve dipstick)	D1 1' ' ''			
Gynecological (GYN)	None (normal period)	Spotting not at time of	Bleeding > spotting			
		normal period	not at time of period			
D. I	NT.	37/4	or very heavy period			
Pulmonary	None	N/A	Yes			
Intracranial haemorrhage	None	N/A	Yes			
Subconjunctival haemorrhage	None	Yes	N/A			

Source:

Appendix 3 Management of Increases in AST, ALT, or Bilirubin

Liver enzyme abnormities or associated symptoms should be managed by adjusting the dose of the study drug or performing additional tests/examinations according to the following instructions. Additional tests/examinations may be performed at the study institution. The investigator should inform the sponsor of the onset of liver function test abnormality specified in "12.4 Management of Abnormal Liver Function Test Values" by the due date specified in "12.4 Management of Abnormal Liver Function Test Values."

R788 is an inhibitor of UGT1A1, the enzyme responsible for the glucuronidation of bilirubin; occasionally an isolated increase in total and unconjugated (indirect) bilirubin may be observed. Study drug should not be interrupted for an isolated increase in total and unconjugated (indirect) bilirubin.

- 1) In the case that subjects meet a), b) and c)
 - a) ALT or AST \geq 3 × ULN
 - b) Total bilirubin $> 2 \times ULN$
 - c) $ALP < 2 \times ULN$
 - (1) Interrupt the study drug and consider withdrawing the subject from the study due to suspected drug-induced liver injury.
 - (2) The investigator will follow the subject until liver function test results and clinical symptoms and findings return to normal or the level of Day 1, or as long as medically indicated.
 - (3) The investigator will investigate the etiology of the event and perform diagnostic examinations.
- 2) In the case that subjects meet a) or b) and have nausea, vomiting, abdominal pain
 - a) ALT or AST $\geq 3 \times ULN$
 - b) Total bilirubin $> 2 \times ULN$
 - (1) Study drug administration should be interrupted.
 - (2) Liver function tests, including bilirubin and alkaline phosphatase should be repeated until ALT/AST or total bilirubin returns to < 1.5 × ULN (the frequency of repeat tests is decided by the investigator).
 - (3) When the ALT/AST or total bilirubin returns to $< 1.5 \times ULN$, the study drug may be restarted at 1 lower dose level.
 - (4) The recurrence of the condition of 2) should be managed in the same manner.

- 3) In the case that subject meet a) or b) and subject is asymptomatic
 - a) ALT or AST $\geq 3 \times ULN$
 - b) Total bilirubin $> 2 \times ULN$
 - (1) Repeat liver function tests immediately, including ALP.
 - (2) If repeat testing shows an increase in ALT/AST or total bilirubin and the ALT/AST value exceeds 5 × ULN, immediately interrupt study drug administration.
 - (3) Liver function tests including ALP will be repeated until ALT, AST, or total bilirubin returns to $< 1.5 \times ULN$ (the frequency of repeat tests is decided by the investigator).
 - (4) When the ALT/AST or total bilirubin returns to $< 1.5 \times ULN$, the study drug may be restarted at 1 lower dose level.
 - (5) The recurrence of the condition of 3) should be managed in the same manner.

Dose Adjustment

Dose reduction				Dose before	Dose escalation		
Dose level -4	Dose level -3	Dose level -2	Dose level	dose increase/ reduction	Dose level +1	Dose level +2	Dose level +3
Interruptio n	100 mg qd	150 mg qd	100 mg bid	150 mg bid	_	_	_
_	Interruptio n	100 mg qd	150 mg qd	100 mg bid	150 mg bid	_	_
_	_	Interruptio n	100 mg qd	150 mg qd	100 mg bid	150 mg bid	_
_	_	_	Interruptio n	100 mg qd	150 mg qd	100 mg bid	150 mg bid

References:

FDA. Guidance for Industry: Drug-induced liver injury: premarketing clinical evaluation. In: FDA,CDER,CBER.http://www.fda.gov/downloads/drugs/guidancecomplianceregulatory information/guidances/ucm174090.pdf: issued July 2009.

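### After suspected drug-induced liver injury (Appendix 3 item 1), restart of R788 falls to the general rule in 8.6.2.2, which takes no account of the cause found

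*Protocol*

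**What the plan says.** Appendix 3 of the protocol sorts liver abnormalities into three items.

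- **Item 1** is the combined pattern: ALT or AST at least 3 × ULN, total bilirubin above 2 × ULN, and ALP below 2 × ULN. Its first action is "Interrupt the study drug and consider withdrawing the subject from the study due to suspected drug-induced liver injury". Its second is follow-up until tests and symptoms are back to normal or to their Day 1 level, or for as long as medically needed. Its third is "The investigator will investigate the etiology of the event and perform diagnostic examinations".
- **Items 2 and 3** cover a rise in either marker, with symptoms (item 2) or without (item 3). Each ends with a restart line: below 1.5 × ULN, "the study drug may be restarted at 1 lower dose level".

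Section 8.6.2.2 lists increases in ALT, AST or bilirubin among the events it governs and points to Appendix 3. It then gives a general rule for any listed event that led to interruption. On recovery, the drug is resumed one level below the dose before interruption, and afterwards it can go up one level if the investigator so decides. The stated exceptions are the floor at 100 mg qd and recurrences of neutropenia or of Grade 3 or 4 diarrhea. The synopsis, under Dosing adjustments, repeats the general rule.

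**The concern.** Item 1 is the most serious liver pattern in the appendix and the only one the protocol labels as suspected drug-induced liver injury. Withdrawal is to be considered but is not required, so a subject can be interrupted, investigated and kept in the study. Item 1 does not say what then happens to dosing, although the two milder items do.

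The work-up in the third action also has no stated consequence for dosing. If it finds no cause other than R788, the text that governs restart reads the same as if it had found an unrelated viral hepatitis. What is at stake is re-exposure, possibly at the original dose, of a subject whose liver injury is most plausibly due to the drug.

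**Working it through.** No sample size, error rate or power is involved. The check is a reading of every text that could govern restart after item 1 is met.

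**Step 1. Does item 1 itself address restart?** It has three actions: interrupt and consider withdrawal; follow up; investigate the cause. None permits, forbids or sets a condition for restart.

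**Step 2. What else could govern a subject who is not withdrawn?**

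| Text | Reaches item 1? | Trigger | Depends on cause? |
|---|---|---|---|
| 8.6.2.2, general restart rule | Yes: it names Appendix 3, and item 1 is not among its exceptions | Recovery | No |
| Synopsis, Dosing adjustments | Yes: it lists the same liver events | Recovery | No |
| 5.3.1 1), withdrawal for an adverse event | Yes, but it only removes the subject | Investigator's judgment | Only through that judgment |
| 12.4 and 12.2 | Yes, for reporting only | Laboratory values or seriousness | No |
| SAP | No restart rule | – | – |

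The general rule is thus the operative text. Its restart sentence is worded as an instruction. Its re-escalation sentence is a permission left to the investigator.

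**Step 3. Where does the general rule lead?** Table 8.6.2.2-1 orders the doses as 150 mg bid, 100 mg bid, 150 mg qd, 100 mg qd. One level down and then one level up gives:

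- 150 mg bid → 100 mg bid → 150 mg bid
- 100 mg bid → 150 mg qd → 100 mg bid
- 150 mg qd → 100 mg qd → 150 mg qd
- 100 mg qd → 100 mg qd at restart, because of the floor

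From each of the three higher doses, one re-escalation returns the subject to the dose at which the injury occurred. From the lowest dose, the restart itself is at that dose.

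**Step 4. Is the sponsor told?** Section 12.4 requires a form within 5 days when AST or ALT is at least 3 × ULN and total bilirubin at least 2 × ULN together. Item 1 requires at least 3 × ULN and above 2 × ULN, so every item 1 case meets 12.4. If the event is judged serious, 12.2 replaces the form and requires notice within 24 hours. Neither section sets a restart condition.

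**Step 5. How often might this arise?** The documents give no frequency for the combined pattern, and none is assumed here. In the overseas Phase III studies (Table 1.4.1-1), ALT increased was reported in 11% and AST increased in 9% of 102 R788 subjects, against 0% for each on placebo. None of these events was severe. Section 1.4.1 lists four treatment-related serious events on R788, none of them hepatic.

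**The case against.** The best defence is that the protocol is not silent. Where an appendix orders interruption without a restart line, 8.6.2.2 supplies the default. Appendix 6 item 1) and item 2)(6) are drafted in the same way. Timing is answered too, because Table 10.15.7-1 defines recovery as resolution of symptoms, normal values or return to baseline, close to the end point of follow-up in item 1. Cause enters earlier: withdrawal is framed around suspected drug injury, the work-up informs that decision, and causality is judged for every event under 10.15.8. Re-exposure with R788 as the only candidate needs an investigator who suspected the drug, found nothing else, and still chose not to withdraw.

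Most of this stands, and it limits the size of the point. It does not remove it. If 8.6.2.2 is the default, then a stated rule provides for restart and allows re-escalation after suspected drug-induced liver injury, with no link to the work-up.

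Three other readings are tempting.

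- **Silence in item 1 means no restart.** Many investigators would act this way, but 8.6.2.2 names Appendix 3 and makes no exception for item 1.
- **Items 2 and 3 also apply.** A subject with both markers raised literally fits "In the case that subjects meet a) or b) and have nausea, vomiting, abdominal pain" or "In the case that subject meet a) or b) and subject is asymptomatic". A reader might infer that recovery of one marker is enough ("When the ALT/AST or total bilirubin returns to" below 1.5 × ULN) and that restarts are unlimited ("The recurrence of the condition of 2) should be managed in the same manner"; "The recurrence of the condition of 3) should be managed in the same manner"). The documents do not support this. Item 3 calls for repeat tests and interrupts only if ALT/AST then exceeds 5 × ULN, which contradicts the immediate interruption in item 1. The overlap with item 2 is only literal; item 1 is the specific rule for the combined pattern. The conjunction follows an either-marker entry test and naturally means whichever marker was raised.
- **8.3.1 4) shows a stricter standard for both markers.** It is an entry criterion for subjects leaving Period I for lack of efficacy, not a restart rule.

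**Conclusion.** The point holds in a limited form. Item 1 has no restart line, so a subject who is not withdrawn falls under 8.6.2.2 and the synopsis. These resume the drug on recovery and allow a step back up at the investigator's decision, without regard to the cause found.

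It is a low-frequency safety improvement that could be made. It arises only after a decision against withdrawal, the sponsor is informed in every case, and re-escalation is discretionary. A reader might take the dose steps above as a measure of harm. They are not: they show where the rule permits dosing to go, and the documents contain no event rate from which to size a risk.

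The conclusion assumes that 8.6.2.2 applies wherever Appendix 3 gives no restart instruction of its own, which is the plainest reading of its reference to that appendix. Isolated bilirubin rises are dealt with separately in the introduction to Appendix 3 and are not affected.

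**What to change.** Add a fourth action to Appendix 3 item 1: do not restart the study drug unless the work-up in (3) identifies a cause other than the study drug. If it does, the drug may be resumed one dose level lower once both ALT/AST and total bilirubin are back to normal or to the Day 1 level, as in (2), with no re-escalation afterwards. In 8.6.2.2 and the synopsis, add to the restart and re-escalation sentences an exception for interruption under Appendix 3 item 1.

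The recovery standard should be that of item 1(2), not the 1.5 × ULN of items 2 and 3, which would be looser for a subject with normal Day 1 values.

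The cost is a few lines of text and no new tests, since the work-up is already required. The downside is that a rare subject who might have been restarted stays off drug and later data are lost. That could include a subject whose bilirubin rise partly reflects inhibition of UGT1A1 by R788, where another cause is hard to establish. If such a subject is withdrawn for the event in Period I, SAP 11.1 counts the subject as a non-responder, which matters somewhat with 16 subjects planned on R788.
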